6.2.2 Selection of Principal Investigators

Pls will be required to demonstrate equipoise, relevant experience and commitment during early stage feasibility assessment. All investigators will have the particular medical expertise necessary to conduct the study in accordance to the protocol and all regulatory and ethical requirements. Written agreement to conduct research as such will be obtained prior to site initiation.

A suitable co-investigator should be identified at each site to deputise in case of PI absence.

7 ELIGIBILITY CRITERIA

The INCA trial aims to recruit 30 patients based on sample size calculations described in Section 14.2. All patients must provide written, informed consent before any study procedures occur (see Section 10.2 for more information regarding the informed consent processes) and must meet all eligibility criteria as described below.

We anticipate that patients who have refractory moderate to severe CRPS will mainly be recruited from the two trial sites (tertiary care). All will have completed conventional treatments (i.e. physiotherapy and drug treatments, see below) for CRPS and some will have failed spinal cord stimulation.

7.1 Inclusion Criteria

Patients eligible for the trial must comply with all of the following at baseline:

- 1. A diagnosis of CRPS I or II according to the Budapest research criteria at the time of assessment for this study.
- 2. First documented diagnosis of Budapest CRPS by a healthcare professional not less than 18 months and not longer than 15 years before the screening assessment. A valid documented diagnosis must either include the term 'Budapest CRPS', or must include the term 'CRPS' and in addition documentation of the presence of signs and symptoms which allow making the Budapest diagnosis from the notes.
- 3. Pain intensity average 6 or greater on a 0-10 point numerical rating scale (NRS) over a minimum of seven consecutive daily entries prior to baseline (0 day) visit, with no single value below 5.
- 4. Completed a previous course of appropriate specialised physiotherapy.
- 5. Poor response or intolerance to at least one anti-neuropathic pain medication such as tricyclic antidepressants or gabapentinoids.
- 6. If a woman of childbearing potential (WOCBP), to be willing to confirm the use of adequate birth control during the trial period unless pregnancy is impossible
- 7. Fertile male patients to be using contraception for the duration of therapy if sexually active with a female partner
- 8. Age 18 years and over.
- 9. Written and informed consent obtained from patient and agreement of patient to comply with the requirements of the study.

Please refer to section 7.4 for contraception and pregnancy testing in relation to Inclusion criteria 6 and 7

7.2 Exclusion Criteria

Any patient meeting any of the criteria listed below at baseline will be excluded from study participation:

- 1. Medical conditions that in the opinion of the study investigator would make it unsafe for participation or can adversely affect outcomes.
- 2. Co-existing pain that in the view of the study doctor may make assessment of outcomes related to refractory moderate to severe CRPS unreliable.
- 3. Ongoing relevant litigation where its conclusion is imminent during the course of the study.
- 4. Medical Contraindications to Anakinra such as moderate/severe or progressive renal impairment (CLCR < 60 ml/min or Estimated Glomerular Filtration Rate (eGFR)<60ml/min/1.73m² or end stage renal disease, including dialysis), or hepatic impairment (defined as any value of transaminases, γ-

glutamyl transpeptidase, or bilirubin greater than 2 times the upper normal limit) or hypersensitivity to anakinra or any of its excipients or to E.coli derived proteins.

- 5. Previous use of Anakinra.
- 6. Current or recent (within 6 months) use of other immunosuppressants or biologics.
- 7. Neutropenia defined as Absolute Neutrophil Count (< 1.5 x 10⁹/l).
- 8. Requirement to receive a live vaccine during the trial duration.
- 9. Active or latent Tuberculosis (TB) infection.
- 10. HIV, Hepatitis B or C carrier.
- 11. Brittle asthma.
- 12. Active malignancy or malignancy within 2 years
- 13. Ongoing alcohol or drug misuse at registration.
- 14. Psychiatric or other mental health disorder which in the opinion of the study investigator may interfere with successful study participation.
- 15. Commencing new therapy for refractory moderate to severe CRPS that may alter the outcome of the trial drug; this includes new pain management program treatment. Equally patients who have completed a pain management program within the past 3 months.
- 16. Subject is pregnant or breastfeeding.
- 17. Patients who have a spinal cord or dorsal root ganglion stimulator whose average pain is less than 6 out of 10 when the stimulator is on.

7.3 Co-registration Guidelines

To avoid potentially confounding issues, ideally participants should not be recruited into other trials during their participation in INCA. Where recruitment into another, non-interventional trial is considered to be appropriate and without having any detrimental effect on the INCA trial this must first be discussed with the LCTC who will contact the CI ([name]).

Individuals who have participated in a research trial of other drug or blood products within 12 months preceding screening will be ineligible for the INCA trial.

7.4 Contraception and pregnancy testing

A WOCBP is defined as fertile, following menarche and until becoming post-menopausal unless permanently sterile. Permanent sterilisation methods include hysterectomy, bilateral salpingectomy and bilateral oophorectomy.

A postmenopausal state is defined as no menses for 12 months without an alternative medical cause. A high follicle stimulating hormone (FSH) level in the postmenopausal range may be used to confirm a postmenopausal state in women not using hormonal contraception or hormonal replacement therapy. However, in the absence of 12 months of amenorrhea, a single FSH measurement is insufficient and confirmation with more than one FSH measurement is required.

Pregnancy tests for eligibility purposes must be from serum or a highly sensitive urine test. Pregnancy test will be completed at screening, 30, 60, 90 and 120 days.

A man is considered fertile after puberty unless permanently sterile by bilateral orchidectomy.

Birth Control Methods which may be considered highly effective include methods that can achieve a failure rate of less than 1% per year when used consistently and correctly:

- 1. Combined (Oestrogen and progesterone containing) hormonal contraception associated with inhibition of ovulation:
- Oral
- Intravaginal
- Transdermal
- 2. Progesterone-only hormonal contraception associated with inhibition of ovulation:
- Oral
- Injectable
- Implantable
- 3. Interuterine device (IUD)
- 4. Interuterine hormonal-releasing system (IUS)
- 5. Bilateral tubal occlusion
- 6. Vasectomised partner provided that partner is the sole sexual partner of the WOCBP trial participant and that the vasectomised partner has received medical assessment of surgical success
- 7. Sexual abstinence-only if refraining from heterosexual intercourse during the entire period of risk associated with the study treatment. The reliability of sexual abstinence needs to be evaluated in relation to the duration of the clinical trial and the preferred and usual lifestyle of the subject.

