10.3 Screening Visit

A screening log of all patients who are approached about the study will be maintained, including patients who decline to attend the screening visit or are not deemed eligible for participation, as this will provide important information for monitoring purposes. The screening log will assign all potential participants with a unique site screening number, which will be made up of a 3-digit sequential number (XXX). This number should be written on all samples and study documentation used prior to registration.

Screening logs will contain information on consented and non-consented patients. The data for those who are non-consented is considered fully anonymous to all individuals outside of the patient's usual clinical care team. Sites will maintain their own trial register linking patients screening and/or randomisation numbers to their identifiers. Under no circumstances will this log be returned to the LCTC.

During the Screening visit the following assessments will be carried out:

- Complete Informed Consent Form
- Screening eligibility assessment
- Patient demographics
- Medical history and examination
- Review of Concomitant Medications
- CRPS History and limb examination
- Limb volume
- Vital signs (weight, height, Heart rate (HR) and Blood pressure (BP))
- Pain severity on a 0-10 (NRS)
- Pregnancy test from all female subjects of child-bearing potential
- Issue pain diary (up to two weeks daily diary: only seven days before visit is required)
- Full blood count and differential.
- Serum biochemistry- Sodium, potassium, urea and creatinine.
- Liver function tests- Bilirubin, ALT, AST, ALP, GGT.
- HIV, Hepatitis B and C screen unless a screen has been done in the 3 months prior to the screening visit
- TB screen as either a Tuberculin Skin Test or TB Interferon-Gamma Release Assay(IGRA) unless a TB screen of either method has been done in the 3 months prior to the screening visit
- Chest X-ray unless one has been done in the last 12 months

Informed consent must be in place before any other trial specific assessments are performed. A screening CRF should be completed but only returned for participants who are later registered in the trial.

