10.4 Registration/Baseline visit (Day 0, visit 1)

Eligibility can only be confirmed by CI or PI or their delegate. Eligibility assessment must not occur until fully informed consent is documented. Eligibility criteria are described in detail in Section 7.

Eligibility confirmation must be documented in the participant's medical notes and then on the trial's Eligibility CRF. Details must include at a minimum who confirmed full eligibility, when this was confirmed, and when the participant was formally entered into the trial.

Eligibility will be confirmed in two stages, i) from information obtained at the screening visit, ii) from the results of pain diaries completed between screening visit and registration visit, and results of screening blood tests, and TB screening where appropriate.

Baseline assessments should be completed as per the Schedule of Assessments (Section 10.7) in order to accurately complete the Baseline CRF and collect the necessary information for the trial analyses. This includes the following assessments:

- Vital signs
- Pain Intensity on a 0-10 NRS with 0 being no pain and 10 being the worst pain experienced, over the past 24hr.
- CRPS Severity score
- PHQ-9
- EQ-5D-5L
- HADS
- BPI
- Mechanical QST this will be completed twice for the purposes of the sub study: once blindfolded and once non-blindfolded with the order decided at random (see section 10.4.1)
- Work status
- Medication use in opioid (Morphine) equivalents

10.4.1 **Sub study Randomisation**

During the baseline visit, participants will be randomised to inform the order in which the baseline mechanical QST assessment should be performed. Randomisation will be via a secure (24-hour) web-based randomisation system controlled centrally by the LCTC. A personal login username and password, provided

by the LCTC, will be required to access the randomisation system; designated research staff will be issued with their personal login and password upon completion of training in the use of the system.

When the system requirements are confirmed, a unique randomisation number will be displayed on a secure webpage along with the allocated sequence for the QST to be completed in. An automated email confirmation will be sent to the authorised randomiser. Note that the randomisation number will not be required as a participant identifier for the purposes of the trial as the randomisation relates to the sub study only.

Randomisation: web access https://ctrc.liv.ac.uk/Randomisation/INCA

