10.5 Registration

Participants will be registered into the trial once:

- a) Fully informed written consent has been obtained (and appropriately documented)
- b) Eligibility criteria have been fulfilled (and eligibility confirmed)
- c) baseline (0 day) assessments have been completed (at least seven days after the screening visit).

At this point participants will be assigned a registration number, made up of the letter R, the 3-digit site code and a 3-digit sequential number (RXXX-XXX). This number should be written on all samples and study documentation used from this point onwards.

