10.6 Intervention

Upon registration into the research trial, participants will be self-taught to administer Anakinra on that day. Anakinra will be dispensed at baseline and at each clinic visit in accordance with the pharmacy manual, with each patient being provided with sufficient Anakinra to inject this once a day as per protocol. It is the responsibility of the PI or delegated research staff to inform the pharmacy department at their centre of impending registrations to ensure there is sufficient supply of the study drug.

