10.7 Schedule for Assessments and Follow-up

All assessments and follow up are to be conducted in line with the Schedule of Assessments below: *Table 4: Schedule of Assessments:*

				Visit 1	Telephone follow up 1	Visit 2	Telephone follow up 2	Visit 3	Telephone follow up 3	Visit 4	Telephone follow up 4	Visit 5	Telephone follow up 5	
		Screening	Pre-baseline Telephone visit	Baseline^	Baseline +2wks	Day 30*	Day 30 +2wks	Day 60*	Day 60 +2wks	Day 90*	Day 90 +2wks	Time Point Day 120*	Day 180#	Premature Discontinuation
Proced	ures													
Signed Form	Consent	Х												
Registr	ation			Х										
Assess Eligibili	ment of ty Criteria	Х		Χ										
History	of Medical (including raphics)	Χ												
Review Concor Medica	mitant	Χ		Х	X	X	Х	Х	Х	Х	Х	Х	Х	х
(Daily a	ntervention after e to day			Х		Х		Х		Х		Х		
	Medical History and examinati on	Х										Х		X***
Clinical Assessment	CRPS History and Limb Examinat ion	Х										Х		X***
Clinical	Vital signs, weight, height, HR and BP	Х		Х		Х		X		Х		Х		X***
	Limb Volume	Х						Х				Х		
applica	or Blood	Х				Х		Х		х		х		
(CXR)	Radiograph and TB testing†	Х												

				Visit 1	Telephone follow up 1	Visit 2	Telephone follow up 2	Visit 3	Telephone follow up 3	Visit 4	Telephone follow up 4	Visit 5	Telephone follow up 5	
		Screening	Pre-baseline Telephone visit	Baseline^	Baseline +2wks	Day 30*	Day 30 +2wks	Day 60*	Day 60 +2wks	Day 90*	Day 90 +2wks	Time Point Day 120*	Day 180#	Premature Discontinuation
TB scre	ening skin test†	Х												
Issue and coll	pain diary lection	Х		Х		Х		Х		Х		Х		
Numerio Score Pain	cal rating for CRPS	Х	Х	X	×	X	X	X	X	X	X	Х	Х	Х
CRPS score	Severity			Х		Х		Х		Х		Х		
EQ5D-5	5L			X		Х		Χ		Х		Х	X	
PHQ-9				Х		X		Χ		Χ		Х		
HADS				X		X		Χ		X		X		
BPI				X		X		Х		Х		X		
Work S	tatus			Х								Х		
QST-bli unblinde				Х								X+		
Global of Chan	Impression ige											Х		
Assessi Adverse	ment of Events			Х	Х	Х	X	Х	Х	Х	Х	Х	Х	Х
Blood sample collection	Clinical Chemistr y/ Hepatic Function	X				Х		X		X		X		X
Blo	Haematol ogy	Х				Х		Х		Х		Х		х
Serology	HIV/Hep atitis B and C‡	х												
Researd	ch Blood	X			/ 6							X~		

Each Time point for follow up schedule can be +/- 3 days.

†unless a TB screen of either method listed has been done in the 3 months prior to the screening visit ‡unless a screen has been done in the 3 months prior to the screening visit

[^]Time between Screening and Baseline should be no more than 14 days.

^{*} Face to face appointment

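### No pregnancy test is scheduled on day 0, when the pregnancy exclusion applies and anakinra starts; the only scheduled pre-dose test is 7 to nominally 14 days old

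*Protocol*

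**What the plan says.** Protocol 7.2 sets the time at which the exclusions apply: "Any patient meeting any of the criteria listed below at baseline will be excluded from study participation". Criterion 16 covers pregnancy and breastfeeding. Treatment begins at the same visit (10.6): "Upon registration into the research trial, participants will be self-taught to administer Anakinra on that day".

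The testing schedule in 7.4 reads: "Pregnancy test will be completed at screening, 30, 60, 90 and 120 days". The screening list in 10.3 matches it: "Pregnancy test from all female subjects of child-bearing potential". The baseline list in 10.4 contains no pregnancy test. The second stage of eligibility confirmation in 10.4 works "from the results of pain diaries completed between screening visit and registration visit, and results of screening blood tests, and TB screening where appropriate". The Table 4 row whose marks match 7.4 has none under Baseline. Its label is damaged in the text available to this review, so the point rests on 7.4, 10.3 and 10.4.

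Two rules fix the age of the screening test at first dose. Section 10.5(c) allows registration only when "baseline (0 day) assessments have been completed (at least seven days after the screening visit"), and a Table 4 footnote adds: "Time between Screening and Baseline should be no more than 14 days".

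**The concern.** The plan tests for pregnancy at all four clinic visits after baseline (days 30, 60, 90 and 120), but not at the visit where the exclusion is applied and the drug is started. A participant whose pregnancy became detectable after the screening test could be registered and dosed while meeting an exclusion. From day 30 a positive result can only end exposure that has already begun.

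The consequences named in the documents are stopping treatment (10.9), notification within 24 hours and follow-up to childbirth (13.8). No fetal risk figure for anakinra is given, so the harm cannot be sized from these documents. No estimate or analysis in the SAP depends on the point.

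**Working it through.** The plan states no figure of its own here. The check is a comparison of sections followed by day arithmetic.

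**1. Does any other provision require a test before the first dose?**
- Table 4 marks eligibility assessment at baseline as well as at screening, but no new pregnancy evidence is specified for it.
- Inclusion 6 (7.1) asks a WOCBP to be willing to confirm adequate birth control during the trial. It requires no test.
- A Table 4 footnote permits extra tests on suspicion. They are optional.
- Section 10.9 allows treatment to be stopped for an exclusion recognised later, which is after exposure.

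None of these requires one.

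**2. Age of the last scheduled test at first dose, G.** The minimum is 7 days (10.5c) and the nominal maximum 14 days (Table 4 footnote, worded as should). With a day-0 test it is 0 days.

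**3. Which pregnancies would a day-0 test add?** Let L be the days from conception to a detectable result. The documents give no value; 7, 10 and 14 are assumed. A pregnancy shows at baseline if conceived at least L days before it, and shows at screening if conceived at least G + L days before baseline. The added detections are those conceived between G + L and L days before baseline, a band G days long.

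The share of conceptions between screening and baseline that a day-0 test would show is max(0, 1 − L/G):

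| | L = 7 | L = 10 | L = 14 |
|---|---|---|---|
| G = 14 | 50% | 29% | 0% |
| G = 7 | 0% | 0% | 0% |

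The band has the same length as the screening-to-baseline interval, so at a constant conception rate these are also the shares of the added detections conceived after screening. In every cell at least half were conceived before screening, and in four of the six cells all were.

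**4. Expected number of added detections** = WOCBP × yearly rate × G/365.
- Yearly rate: 1%, the limit that 7.4 gives for highly effective methods.
- WOCBP: 5 assumed at the low end. The high end is 30 × 3/4 = 22.5, which treats every woman at the 3:1 ratio in 5.1 as a WOCBP.

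| WOCBP | G = 7 | G = 14 |
|---|---|---|
| 5 | 5 × 0.01 × 7/365 = 0.00096 | 5 × 0.01 × 14/365 = 0.0019 |
| 22.5 | 22.5 × 0.01 × 7/365 = 0.0043 | 22.5 × 0.01 × 14/365 = 0.0086 |

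Per WOCBP: 0.01 × 7/365 = 0.019% to 0.01 × 14/365 = 0.038%. A deliberately extreme case, with a 10% rate that appears nowhere in the documents and every woman a WOCBP, gives 22.5 × 0.10 × 14/365 = 0.086.

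**5. Doses before the next scheduled test.** That test is at day 30, and "Each Time point for follow up schedule can be +/- 3 days". One dose daily from day 0 gives 30 − 3 = 27 to 30 + 3 = 33 doses. This is a maximum, because it assumes that nothing is noticed earlier.

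**The case against.** The strongest reply is that the schedule is coherent and the effect negligible. Much of it stands.

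- A reader might infer that 7.2 contradicts 7.4. It does not. Section 10.4 relies openly on screening results, the neutrophil, renal and liver exclusions also rest on screening samples, and applying criteria at baseline does not promise a same-day test for any of them. The short window is itself a control.
- A reader might infer that day 0 is the only chance to prevent exposure. A positive screening test prevents it too; the statement holds only for visits after screening.
- A reader might infer that a day-0 test saves 27 to 33 doses per pregnancy found. The telephone call two weeks after baseline assesses adverse events, pregnancy is a recordable event (13.7), and tests on suspicion are allowed, so an unrecognised pregnancy could come to light sooner. These routes are discretionary, so they lower the figure without replacing a test.
- A reader might infer that the test closes the gap between screening and baseline. It would show none to half of the conceptions in that interval, depending on the assumed lag.
- The 1% rate does not fit well. It describes highly effective methods used consistently and correctly, and the trial's contraception requirement covers the trial period, whereas most added detections would be conceived before screening. The true rate there could be higher or lower.
- On size, even 0.0086 means one added detection in about 1/0.0086 ≈ 116 trials like this one. Section 5.1 gives a mean age of 50 to 60 years for people with CRPS, which makes 22.5 WOCBP unlikely.

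What the reply does not remove is that no provision requires a negative test close to the first dose, and that one could be had at a visit already taking place.

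**Conclusion.** The gap is real and minor. The only scheduled pre-dose pregnancy test is 7 to nominally 14 days old when anakinra starts. The documents support calling this a missed low-cost safeguard. They do not support calling it an inconsistency, a material risk to the cohort or a threat to the trial's results.

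The expected gain is about 0.001 to 0.009 added detections, given an assumed 1% yearly rate and an assumed 5 to 22.5 WOCBP. Which conceptions those would be depends on an assumed detection lag of 7 to 14 days. The case for acting rests on the low cost and on the value of preventing exposure instead of interrupting it.

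**What to change.** In 7.4, in the baseline list in 10.4 and in the Baseline column of Table 4, add a highly sensitive urine pregnancy test for WOCBP at the baseline visit. Require a negative result before registration and the first dose. Keep the screening test, which spares a pregnant participant the rest of the run-in.

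The cost is one urine test per WOCBP, of a type 7.4 already accepts for eligibility: six scheduled tests each instead of five, and at most about 23 more in the trial (22.5 rounded up). No extra visit or blood draw is needed, only a short amendment. The latest protocol change was a two-week recruitment extension, so recruitment may already be closed. In that case, carry the baseline test into the schedule of the planned randomised trial.
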